## 310 **6. INCLUSION/EXCLUSION CRITERIA**

311

### 312 **6.1. Inclusion criteria:**

- 313 - Type 2 diabetic patients ( $\geq 18$  years of age) with more than 5 years of evolution of the disease,
- 314 - treatment with **metformin** ( $\pm$  sulfonylurea) at a stable dose for at least the previous 3 months,
- 315 - HbA1c  $\geq 7.0$  and  $\leq 10.0\%$ ,
- 316 - body mass index  $\geq 30$  Kg/m^2,
- 317 - no known lung disease,
- 318 - baseline reduction in FEV1 equal or higher than 10% in the percentage predicted value,
- 319 - provision of an informed consent form signed and personally dated by the patient.

320

### 321 **6.2. Exclusion criteria:**

- 322 - type 1 diabetes,
- 323 - treatment with insulin, dipeptidyl peptidase-4 inhibitors, and/or pioglitazone,
- 324 - history of smoking habit,
- 325 - chronic pulmonary obstructive disease,
- 326 - sleep-breathing disorders that require CPAP (continuous positive airway pressure) therapy,
- 327 - asthma,
- 328 - previous bariatric surgery,
- 329 - cardiovascular disease, heart failure, and/or stroke,

- 330 - chest wall diseases,
- 331 - serum creatinine > 1.7 mg/dl,
- 332 - abnormal *liver function test* (ALT/AST levels greater than twice the upper limit of normal),
- 333 - *history of acute or chronic pancreatitis*,
- 334 - *history or family history of medullary carcinoma or the thyroid or MEN 2*,
- 335 - female of child-bearing potential who is pregnant, breast-feeding or intends to become pregnant
- 336 - females of childbearing potential who are not using adequate contraceptive methods (as
- 337 required by local law or practice).

338

339 **6.3. Concomitant therapies:** the next concomitant therapies will be included in the exclusion criteria  
340 because of their effects on pulmonary function or glucose metabolism. Patients enrolled in the study who  
341 initiate any of these concomitant treatments will be also excluded from the study:

- 342 - insulin
- 343 - antidiabetic agents others than metformin or sulfonylureas
- 344 - inhaled bronchodilator drugs or teophillin
- 345 - CPAP (continuous positive airway pressure) therapy
- 346 - oral corticosteroids.

347

348

## 349 **7. PRIMARY AND SECONDARY MEASURES**

350

351 All these measurements will be performed through a forced spirometry (DATOSPIR touch, Sibel S.A.)  
352 and a non-attended ambulatory respiratory polygraphy ("Sleep&Go", Sibel S.A.) devices. Blood  
353 specimens will be recollected, processed and stored in each centre, and evaluations will be evaluated in  
354 a central laboratory.

355

356 **7.1. Primary efficacy measure:** Forced expiratory volume in 1 s (FEV1). We have selected this variable  
357 because in our previous studies the main abnormality detected in type 2 diabetic patients was a decrease  
358 in FEV 1 (*Lecube et al. Diabetologia 2010; Lecube et al. Diabetes Metab Res Rev 2010*). In this regard, it  
359 should be emphasized that a 10% decrease in FEV1 has been associated with a 12% increase in all  
360 cause mortality in diabetic patients (*Davis et al. Diabetes Care 2004*).

361

### 362 **7.2. Secondary efficacy measures:**

- 363 - Other parameters drawn from a forced spirometry:
  - 364 - Forced vital capacity (FVC)
  - 365 - Maximum mid-expiratory flow (FEF25-75)
  - 366 - FEV1 to FVC ratio

- 367 - Parameters from static pulmonary volume measurements:
- 368 - Residual volume (RV)
- 369 - Total lung capacity (TLC)
- 370 - Residual functional capacity (RFC)
- 371 - Transfer factor of the lungs for carbon monoxide (TLCO)
- 372 - Data from the six-minute walking test
- 373 - Parameters from a previously validated non-attended respiratory polygraphy
- 374 - apnea-hypopnea index (AHI)
- 375 - cumulative percentage of time spent with oxygen saturations below 90% (CT90)
- 376 - Changes from basal in serum levels of surfactant A protein,
- 377 - Data from the study of inflammation markers in the exhaled breath concentrate: nitric oxide, pH,
- 378 and concentration of nitrites, nitrates and isoprostane

379

### 380 **7.3. Other variables to be evaluated:**

- 381 - Anthropometric data: weight, height, waist circumference, and neck circumference
- 382 - Daytime sleepiness through the *Epworth Sleepiness Test*
- 383 - Fasting blood glucose, HbA1c, fructosamine, fasting insulin, and insulin resistance measured by
- 384 HOMA-IR.

385

386

## 387 **8. SAMPLE SIZE CALCULATION**

388

389 The inclusion of 50 patients will achieve a 80% of statistical power ( $\beta=0.2$ ) to detect a significant increase,  
390 due to the treatment, in the FEV1 levels of at least 20%, assuming a baseline expected values of FEV1  
391 for untreated patients of  $88.4 \pm 19.7$  [as previously reported by Lecube et al (Diabetologia 2010)] and using  
392 and ANOVA test to specifically assess the effect in a cross-over design, setting the threshold for statistical  
393 significance at 5% ( $\alpha=0.05$ , one sided). For this computation, the within mean square error of the ANOVA  
394 test for repeated measurements was calculated as  $\sqrt{2 \times (19.7^2)} = 27.86$ . Sample size will be increased in  
395 10 patients according to an expected drop-out rate of 20%. Hence, a total of 60 patients will be included  
396 in the cross-over randomized trial. In addition, in order to avoid unexpected changes in the final sample  
397 size, we will recruit only patients with a baseline decrease in FEV1 equal or higher than 10% in the  
398 percentage predicted value.

399 However, data regarding factors to be analysed in the present project (for example, levels of  
400 serum surfactant A protein and parameters measured in the exhaled air) are lacking and, therefore, to  
401 give ourselves a safety margin we have increased the sample size. Hence, we hope that the number of  
402 76 patients will be sufficient to demonstrate our hypothesis.

403

404

405 **9. STATISTICAL ANALYSIS**

406

407 First, a homogeneity analysis will be undergone to compare patients in both groups (A and B) with  
408 regards to basal clinical and anthropometric variables. Mean (and standard deviation) and frequency (and  
409 percentage) will be used to describe quantitative and qualitative variables respectively, using Mann-  
410 Whitney test for categorical variables to assess the differences between groups. Second, the effect of the  
411 treatment will be evaluated using an ANOVA test with repeated measures, also adjusting for the potential  
412 carry-over effect and those potential confounders detected in the homogeneity analysis, using for this  
413 purposed mixed linear models. Third, similar analysis will be performed to assess the effect of the  
414 treatment on the secondary outcomes. All analysis will be obtained using R statistical package and  
415 threshold for statistical significance will be set at 0.05.

416

417 **10. DATA MANAGEMENT**

418

419 Data management is always the responsibility of the primary investigator. Data management will be  
420 delegated under an agreement of transfer of responsibilities to an external Contract Research  
421 Organisation (CRO). Appropriate measures, including encryption of data files containing person  
422 identifiable data, will be used to ensure confidentiality of patients data, when they are transmitted over  
423 open networks.

424

425 An electronic Case Report Form (eCRF) that accurately represents the protocol of the clinical trial will be  
426 designed and developed by the CRO to collect the specific data.

427

428 The primary investigators of each center will fulfill the sponsor responsibilities detailed in the Spanish  
429 legislation as well as in the Good Clinical Practices of the ICH. To prevent patient confidentiality each  
430 patient will be identified with a unique code, this will be the only identifiable information that will be  
431 recorded in the eCRF. No patient initials will be recorded.

432

433 Monitors designated by the CRO will be responsible for contacting and visiting the investigators for the  
434 purpose of inspecting the facilities and, upon request, inspecting the various records of the clinical study  
435 (eg, case report forms and other pertinent data) to provide that patient confidentiality is respected. The  
436 monitor will also be responsible for verifying the eCRF at regular intervals throughout the study to verify  
437 adherence to the protocol: completeness, accuracy, and consistency of the data; and adherence to local  
438 regulations on the conduct of clinical research.

439

440

441 **11. TIMELINES**

442

443 **Overall study duration:** 24 months

444 **Treatment duration:** 14 weeks

445 **Enrollment period:** 18 months

446 **Anticipated date of first patient visit:** January 18, 2016 (or as soon as contract will be signed)

447 **Anticipated date that first patient enters treatment:** January 25, 2016

448 **Anticipated date that last patient enters trial:** September 26, 2016

449 **Anticipated date that last patient enters treatment:** October 3, 2016

450 **Anticipated date of the final last patient visit:** January 16, 2017

451 **Anticipated date of first manuscript submitted:** May 1, 2017

452 **12. TRIAL SUPPLIES**

453

454 Trial supplies comprise trial products and auxiliary supplies:

455

456 **12.1 Trial products:** Trial products comprise investigational trial products. The following trial products for  
457 s.c. injection will be provided by Novo Nordisk:

458 . liraglutide 6 mg/mL, 3 mL pre-filled pen-injector

459 . liraglutide placebo 6 mg/mL, 3 mL pre-filled pen-injector.

460

461 Patients will be instructed **when randomised and ready to start the trial** in administration of s.c. injection of  
462 trial product in order to ensure patient's willingness and ability to self-inject.

463

464 Liraglutide, both active drug and placebo will be **visually identical**.

465

466 Novo Nordisk will supply trial product and DFU to the primary investigator located at Hospital Univesitari  
467 Arnau de Vilanova de Lleida (Spain). Therefore, primary investigator will ensure to supply with sufficient  
468 trial products to the four other sites.

469

470 **12.2. Auxiliary supplies:** Novo Nordisk will supply directions for use devices, whereas needles for pre-  
471 filled pen systems will be provided by the primary sponsor.

472

473 **12.3 Labelling:** Labelling of the investigational medicinal products will be in accordance with local law  
474 and trial requirements.

475

476 **12.4. Storage:** The investigator from each centre must ensure the availability of proper storage  
477 conditions, and record and evaluate the temperature. The investigator from each centre must inform  
478 Primary Investigator immediately if any trial product has been stored outside defined conditions (eg,  
479 outside temperature range).

480

481 Trial products stored outside the temperature range for more than fifteen minutes are not to be used and  
482 must be stored separately within allowed temperature range until after evaluation of condition. Evaluation  
483 will be performed by Novo Nordisk. Trial products that have been stored improperly must not be  
484 dispensed to any patient before it has been re-evaluated and approved for further use.

485

486 Returned trial products (unused, partly used or used including empty packaging material) must be stored  
487 separately from non-allocated trial products.

488

489 The temperature during storage should be monitored by a calibrated, stationary and continuously  
490 recording system. A temperature log must be kept to document storage within the right temperature  
491 interval and storage facilities should be checked frequently.

492

493 **Storage conditions:** Not in use, liraglutide both active drug and placebo must be store in a refrigerator  
494 between 2°C and 8°C, and must not be exposed to excessive heat or direct sunlight

495

496 **In-use conditions:** Liraglutide both active drug and placebo must be stored below 30°C or in a  
497 refrigerator (2°C-8°C), protected from light, not freezed, and used within 1 month.

498

499 **12.5. Drug accountability and destruction:** The trial products will be dispensed to each patient as  
500 required according to treatment group. A total DUN list provided by Novo Nordisk to the primary  
501 investigator will be used to link randomisation codes to treatments. A blinded randomisation list will be  
502 created by our own statisticians. Different parts of the code list will be allocated to the other four  
503 participant trial sites, and when a patient will be randomised, a randomisation code will be assigned from  
504 this list. The correct DUN must be dispensed to the patient.

505

506 The investigator from each centre is responsible for ensuring that:

- 507 . trial product is not dispensed to any person not included in the trial,
- 508 . drug accountability,
- 509 . patients are instructed to return all used, partly used and unused trial product including empty  
510 packaging material at each dispensing visit and at End of Treatment visit,
- 511 . all returned trial products is kept and storage separately from non-allocated trial products.

512

513 Destruction of trial products will be done according to local law after accountability is finalised at site and  
514 reconciled by monitor. Destruction of trial products must be documented.

515

516

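### The 50 patients in section 8 do not follow from its own inputs for the crossover test it names (14 to 33 would do, one-sided), and 60 and 76 mean different things in different sections

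*Combined protocol and SAP*

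**What the plan says.** **Section 8.** "The inclusion of 50 patients will achieve a 80% of statistical power" for an FEV1 increase, "due to the treatment, in the FEV1 levels of at least 20%, assuming a baseline expected values of FEV1" of 88.4 with SD 19.7. The unit is not stated; I read it as percent predicted. The test is described as "and ANOVA test to specifically assess the effect in a cross-over design, setting the threshold for statistical" significance at 5%, one-sided. The error term is introduced with "For this computation, the within mean square error of the ANOVA" and computed as √(2 × 19.7²) = 27.86. For drop-out the plan adds "10 patients according to an expected drop-out rate of 20%. Hence, a total of 60 patients will be included". It then raises the number to 76 because data on some other outcomes are lacking: "give ourselves a safety margin we have increased the sample size. Hence, we hope that the number of" 76 is enough.

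**Section 9.** The "treatment will be evaluated using an ANOVA test with repeated measures, also adjusting for the potential" "carry-over effect and those potential confounders detected in the homogeneity analysis", through mixed linear models. The significance threshold is 0.05 with no side given.

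**Section 1.5.** Sixty patients are needed at study end. A 20% drop-out takes this to 76 included. The reader is sent to point 9 for details.

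**Section 5.3.8.** The 76 are called screened patients, yet are placed at the end of the study.

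**The concern.** The sentence in section 8 is the plan's only power statement for the primary outcome. If its number does not follow from its inputs, a reader cannot tell what difference the trial can detect at 80% power, with which test, or at which alpha. A null result could not then be set against a known detectable difference. The conflicting meanings of 60 and 76 also leave open whether 50 or 60 patients must complete.

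Two features raised the doubt. First, √(2 × 19.7²) is the SD of a difference between two uncorrelated values. It is not a within-patient mean square error, and no within-patient correlation is given although that correlation governs crossover precision. Second, section 8 is not tied to the model in section 9, where a carry-over term can remove the crossover gain.

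**Working it through.** **Inputs (section 8).** Mean 88.4, SD 19.7, error term 27.86, one-sided alpha 0.05, power 80%. The 20% is either relative, 0.20 × 88.4 = 17.68 points, or 20 absolute points.

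**1. Crossover test as named.** Power is P(T > t[1−α, n−2]), where T is non-central t with n−2 degrees of freedom and non-centrality (difference / SD of difference) × √n. The 27.86 can be read in two ways:
- as the SD of the within-patient difference; or
- as the root within-patient error, so that the SD of the difference is √2 × 27.86 = 39.4.

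| SD of difference | Difference (points) | n one-sided (power) | n two-sided | Power at n = 50, one-sided / two-sided |
|---|---|---|---|---|
| 27.86 | 17.68 | 17 (0.803) | 22 | 0.997 / 0.993 |
| 27.86 | 20 | 14 (0.812) | 18 | 0.9996 / 0.999 |
| 39.4 | 17.68 | 33 (0.809) | 41 | 0.931 / 0.875 |
| 39.4 | 20 | 26 (0.808) | 33 | 0.971 / 0.940 |

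No row gives 50. Run the other way, 50 patients at 80% power one-sided correspond to 9.9 points (SD 27.86) or 14.1 points (SD 39.4).

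**2. What does return 50.** Two routes do, and each contradicts the text:
- An unpaired two-group t-test of 20 points with SD 27.86, one-sided: 25 per group, power 0.804. The test is not the one named. It also needs the 20% read as absolute points, since 17.68 points needs 32 per group, 64 in all.
- A crossover test of 10 points with SD of difference 27.86, one-sided: n = 50, power 0.804. The effect is not the one stated.

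The plan does not show which was used.

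**3. Link to section 9.** Take 60 completers (30 per sequence) and SD 19.7; the within-patient correlation ρ is an assumption. Detectable differences are at 80% power, one-sided / two-sided.
- No carry-over term: SE = 19.7 × √(2(1−ρ)/60). At ρ = 0 the SE is 3.60 and the detectable difference 9.0 / 10.2 points. At ρ = 0.5 the SE is 2.54 and the difference 6.4 / 7.2 points.
- Carry-over term, no period baselines: generalised least squares gives SE 5.09 at ρ = 0, 0.5 and 0.8. This equals the period-1 between-group SE, 19.7 × √(2/30). The detectable difference is 12.8 / 14.5 points at any ρ.

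For 17.68 points, power from the period-1 contrast alone is 0.931 / 0.875 with 50 patients and 0.963 / 0.928 with 60.

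**4. Drop-out.** Section 8: 60 × 0.8 = 48, below 50; the correct inflation is 50/0.8 = 62.5, so 63. Section 1.5: 60/0.8 = 75 and 76 × 0.8 = 60.8, so 60 completers and 76 randomised agree with each other.

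**5. Counts side by side.**

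| Section | Meaning of 60 | Meaning of 76 |
|---|---|---|
| 1.5 | completers | included, to allow for 20% drop-out |
| 5.3.8 | – | screened, at study end |
| 8 | included, after adding drop-out to 50 | margin for outcomes without prior data |

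Point 9, to which section 1.5 refers, holds no sample size; the calculation is in section 8.

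**The case against.** The strongest reply is that nothing is at risk for the stated effect. On the plan's own inputs, 50 patients give at least 93% one-sided power and at least 87% two-sided, even if only period 1 is used. All three sections end on 76, which leaves 60.8 patients after 20% loss and so absorbs the three-patient drop-out shortfall. This stands, and it is why no change in enrolment is asked for.

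A second reply is that the carry-over figures are pessimistic. Section 5.3.11 schedules expiratory flows at basal and at week 11, so period baselines will exist. This stands in part. A model using all four FEV1 measurements, with equal correlations, no baseline difference between sequences and carry-over terms at weeks 11 and 18, gives SE 4.41 and detectable differences of 11.1 / 12.6 points at an assumed ρ of 0.5. At ρ = 0.8 they are 7.7 / 8.7. There is no gain at ρ = 0, and the gain at 0.5 is lost if a sequence effect is also fitted. Section 9 does not say whether these baselines enter the model, so the precision remains undefined.

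A third reply is that the plan sets no 10-point target. That is correct. Differences of that size matter here only because 50 patients at 80% power imply them, and because at that size the choice of model decides whether 80% is reached.

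**Conclusion.** The concern holds. The sample size of 50 cannot be obtained from section 8's inputs with the crossover test it names: 14 to 33 patients suffice one-sided and 18 to 41 two-sided. These ranges cover both readings of the 20% and both readings of 27.86, and they keep the plan's SD of 19.7 with zero within-patient correlation. The error term is mislabelled, the drop-out allowance falls short by three patients (60 against 63), and 60 and 76 carry conflicting meanings.

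The error makes the trial larger than the stated FEV1 effect requires, not smaller. What is lost is a usable statement of the detectable difference. With 60 completers it runs from 6.4 points (no carry-over term, ρ = 0.5, one-sided) to 14.5 points (carry-over term, no period baselines, two-sided). It should be fixed, at little cost.

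**What to change.** 1. **Section 8.** Recompute the power sentence for the model section 9 will use, for example: *With N completers, the 2×2 crossover analysed by the section 9 model (with / without a carry-over term) has 80% power at alpha 0.05 (one- / two-sided) to detect a difference of D points in FEV1 percent predicted, assuming SD 19.7 and within-patient correlation ρ of [range], so that the SD of the within-patient difference is 19.7 × √(2(1−ρ)).* If the carry-over term stays and period baselines are not used, replace the last clause with the period-1 standard error, 19.7 × √(4/N). Say whether the 20% is relative or in points.
2. **Section 9.** State the same side of alpha, whether treatment is estimated with the carry-over term in the model, and whether basal and week 11 FEV1 serve as period baselines.
3. **SD.** Note that 19.7 comes from an earlier sample and that the plan does not say the FEV1 limit in section 6.1 applied there, so the SD in enrolled patients may differ.
4. **Counts.** Inflate by n/(1 − 0.2) and give one set of completer and randomised numbers in sections 1.5, 5.3.8 and 8. Sixty completers and 76 randomised is arithmetically consistent. Correct the word screened in 5.3.8 and point section 1.5 to section 8.

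Cost: one recalculation and some wording; no extra patients or procedures.

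### The 20% FEV1 target in section 8 is unjustified, has no stated unit and does not match the stated 80% power with 50 patients, which corresponds to about 10 points; power for a 10% gain is not given

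*Combined protocol and SAP*

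**What the plan says.** Section 8 contains the only power statement in the protocol: "The inclusion of 50 patients will achieve a 80% of statistical power", one-sided at 5%, for an FEV1 increase "due to the treatment, in the FEV1 levels of at least 20%, assuming a baseline expected values of FEV1" in untreated patients of 88.4 ± 19.7. The test is a cross-over ANOVA, and its error term is given as √(2 × 19.7²) = 27.86. No unit is printed for 88.4, and no reason is given for the 20%.

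The number is then raised to 60 ("10 patients according to an expected drop-out rate of 20"%) and to 76 as a safety margin. Section 1.5 instead counts 60 patients at the end of the study and 76 included, so both 50 and 60 completers have a basis in the text.

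Three other places bear on the target:
- **Section 7.1** supports the choice of FEV1 with the remark that it "should be emphasized that a 10% decrease in FEV1 has been associated with a 12% increase in all"-cause mortality. Section 2.2 makes the same point.
- **Section 6.1** requires a "baseline reduction in FEV1 equal or higher than 10% in the percentage predicted value", and section 8 repeats this.
- **Section 9** says only that the "threshold for statistical significance will be set at 0.05". It gives no sidedness and no rule for reading a non-significant result.

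**The concern.** A power statement tells the reader which effect a negative trial argues against. Here the named effect is large, unexplained and open to two readings. At the planning mean it passes the predicted normal value, and it is double the only FEV1 change to which the protocol attaches prognostic weight. No power is given for anything smaller.

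The named effect also does not lead to the number of patients printed beside it. A reader therefore cannot tell which effect the trial was sized for. A non-significant FEV1 result could be reported as a null finding from a trial with 80% power, although the protocol never says what chance it had of detecting a 10% gain.

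**Working it through.** **Inputs, all from section 8 unless noted:** mean 88.4, SD 19.7, error term 27.86, n = 50, one-sided α = 0.05, power 80%; 60 completers from section 1.5; entry limit from section 6.1, read as 90% predicted or lower. Reading 88.4 as % predicted is an inference from that criterion.

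**1. The error term.** For within-patient correlation r, the SD of the within-patient difference is SDd = 19.7 × √(2(1 − r)). With r = 0 this is 19.7 × √2 = 27.86, the printed figure. Section 8 nevertheless labels it the within mean square error of the ANOVA. If it is the per-period error SD, SDd = 27.86 × √2 = 39.4.

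**2. The target.**
- Relative reading: 0.20 × 88.4 = 17.68, and 88.4 + 17.68 = 106.1. The gap to 100 is 11.6, so the target is 17.68 / 11.6 = 1.5 times the gap.
- Reading in points: 88.4 + 20 = 108.4.

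**3. Does 17.68 give 50?** n = ((1.645 + 0.842) × SDd / δ)², one-sided.
- SDd 27.86: 15.35, so 16 (17 by the t distribution).
- SDd 39.4: 30.7, so 31 (33 by t).
- Two-sample formulas give totals of 62 to 64 (SD 27.86) or 32 to 34 (SD 19.7).
- Two-sided, the four ranges are 20–22, 39–41, 78–80 and 40–42.

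None of these is 50.

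**4. What does give 50?** With SDd 27.86 and δ = 10 points, n = 47.99, so 48 (50 by t). A two-sample formula with SD 27.86 and δ = 20 points also gives 48 (50 by t). These are the same arithmetic, because a comparison of period differences between sequences estimates 2δ. The documents do not say which was used.

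**5. Power with 50 patients** (noncentral t, 48 df, noncentrality δ√n / SDd, one-sided).

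| Effect | SDd 27.86 | SDd 39.4 |
|---|---|---|
| 17.68 points (20%) | 99.7% | 93% |
| 10 points (11.3% of 88.4) | 80.4% | 55% |

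**6. Power for a 10% gain** (0.10 × 88.4 = 8.84 points), 50 / 60 completers.

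| SDd | One-sided 5% | Two-sided 5% |
|---|---|---|
| 19.7 (assumed r = 0.5) | 93% / 96% | 87% / 93% |
| 27.86 (r = 0) | 72% / 78% | 59% / 68% |
| 39.4 (27.86 as per-period error) | 47% / 53% | 34% / 40% |

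The last row follows from section 8's label. With a total SD of 19.7 it would need r = −1, so it is an outer bound, not a likely value.

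**7. The enrolled population.** A 20% gain passes 100 only from a baseline above 100 / 1.2 = 83.3. If FEV1 is assumed normal (88.4, SD 19.7) and cut at 90, the enrolled mean is about 73.7. A 20% gain is then 14.7 points and ends at about 88.4. The planning mean therefore does not describe the patients whom section 6.1 admits.

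**The case against.** The strongest reply is that the planned number is not shown to be too small. The calculation, as distinct from the sentence, has 80% power for about 10 points, close to the 10% that the protocol emphasises. With a within-patient correlation of 0.5, 50 completers give 93% one-sided power for 8.84 points. This stands, and it is why the fix leaves the sample size alone. It does not defend the printed target, which disagrees with the calculation beside it.

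Three stronger readings are tempting, and the documents support none of them:

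- **That the hypothesis cannot produce a 20% gain.** Section 3 gives neither a size nor a ceiling, and 100% predicted is a reference value, not a biological limit.
- **That 20% exceeds the deficit of the enrolled patients.** It exceeds the gap at the planning mean only. Under the truncated-normal assumption the enrolled deficit is about 26.3 points, and about 75% of enrolled patients would start at or below 83.3.
- **That 10% is a declared minimal important difference.** Sections 2.2 and 7.1 report an observational association of a decrease with mortality. They do not define a treatment gain worth detecting, and they do not say whether 10% is relative or in points.

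**Conclusion.** The point holds as a mismatch within section 8 and a gap in what is reported. The 20% target has no justification or unit, and under section 8's own error term it does not produce 50 patients at 80% power. The effect that matches is about 10 points, provided that 27.86 is the SD of the within-patient difference. Power for a 10% gain is unstated. On a one-sided test with 50 completers it runs from 47% to 93% over the three readings of the error term.

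The 106.1 comparison rests on reading 88.4 as % predicted and 20% as relative. The enrolled mean of about 73.7 rests on an assumed normal distribution cut at 90. Neither assumption is needed for the mismatch between target and power: 20 points would fit even less well in the cross-over calculation, needing 12 patients (14 by t) with SDd 27.86. One should not conclude that the trial can detect only an implausible effect.

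**What to change.** Keep the sample size.

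**Section 8**
- Replace the 20% target with the effect that the calculation supports, about 10 points, and give its unit.
- State what 27.86 represents and which within-patient correlation it assumes. If SDd is not 27.86, the effect with 80% one-sided power changes in proportion. By the normal approximation with 50 patients it is 2.486 × 19.7 / √50 = 6.9 points, or 2.486 × 39.4 / √50 = 13.9 points.
- Report power for a 10% gain (8.84 points) with 50 and 60 completers over the range in the working.
- Note that the planning mean of 88.4 does not reflect the entry criterion of at least a 10% reduction.

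**Section 9**
- Report the FEV1 treatment difference with its confidence interval.
- Describe a non-significant result as showing no relevant effect only if the interval excludes the restated target.

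The cost is wording in two sections, with no extra patients and no change in procedures. The downside is that the stated power for a 10% gain may be well below 80%, depending on the within-patient SD.
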